5.3.2 Analysis of primary outcome data

a) This study is non-inferiority trial design, and the primary outcome is the rate of OS at 5 years. The hypothesis is as follows:

Hypothesis: Let π_1 denote the rate of OS at 5 years in the open surgery group, and let π_2 denote the rate of OS at 5 years in the minimally invasive surgery group, the non-inferiority margin =8%. The null hypothesis is $H_0: \pi_1 - \pi_2 \geq$ versus the alternative hypothesis is $H_1: \pi_1 - \pi_2 <$.

b) The curves of OS at 5 years will be estimated using the Kaplan-Meier method. The logrank test will be used to test the above hypothesis, the 5-year OS rate difference and its 95% confidence interval (CI) for the comparison between the two groups will be estimated. The minimally invasive surgery will be considered non-inferior to the open surgery if the one-sided 95% upper limit is less than , where = 8%, the predetermined non-inferiority margin.

c) Covariate adjusted analysis:

An analysis of the primary outcome adjusting for the blood loss during operation, operative duration, and postoperative pain score will be performed using Cox proportional hazards regression model. The hazard ratio of 5-year OS and 95% CI will be estimated.

d) Subgroup analysis:

We will stratify by tumour staging, and perform Cox proportional hazards regression model to estimate the hazard ratio and 95% CI of the 5-year OS.

e) Sensitivity analysis:

A sensitivity analysis of the primary outcome will be performed using the PP strategy.

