3.12 Sample size

This study uses a non-inferiority trial design, and the primary outcome is the rate of OS at 5 years. The sample size is calculated based on the difference between the two groups of 5-year OS rate. The 5-year OS rate of the patients in the open surgery group is estimated to be 72% based on the previous clinical data from our hospital.

Based on the assumptions of (i) the 5-year OS rate of 72% in the open surgery group, (ii) a non-inferiority margin of 8%, (iii) 80% power, and (iv) a one-sided alpha of 0.025, the sample size estimation resulted in 495 subjects per group (calculated with SAS software, version 9.4). Considering a 10% drop-out rate and the randomization scheme with block size of 6, a total of 1104 subjects should be randomized (552 per group).

3.13 Recruitment methods:

The study team centers will advertise this study at their cervical cancer clinic. If the patients are interested, they will be further introduced in detail about the study background, randomization and surgical procedures, and the patients can voluntarily choose whether to participate in the trial. After patients sign the informed consent forms, members of the study team will review their eligibility according to the inclusion and exclusion criteria. Patients will then be randomized to receive either of the surgical

procedures. Finally, the patients will be followed up according to the follow-up schedule.

IV. Allocation, Blinding and Unblinding

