5.3.3 Secondary outcome analysis

a) The rate of PFS at 5 years:

Cox proportional hazards model will be used to estimate the hazard ratio and 95% CI for the effect of treatment on the 5-year PFS rate.

b) Analysis of continuous outcomes:

The continuous outcomes include operative duration, anesthesia time, blood loss during operation, postoperative pain score and postoperative hospital stay. The outcomes with normal distribution will be summarised using mean and standard deviation (SD), while the outcomes with non-normal distribution will be summarised using median and interquartile. The differences in the outcomes and 95% CIs will be analysed by generalised linear model (GLM) with treatment as fixed effect and with normal distribution and identity link function.

c) Analysis of binary outcomes:

The intraoperative complications, postoperative complications, one-month and one-year postoperative quality of life and sexual life will be treated as binary outcomes, and will

be summarised by number (%) of participants with the event. The differences in the outcomes and 95% CIs will be analysed by GLM with treatment as fixed effect and with binomial distribution and identity link function.

d) Interim analysis

The O'Brien Fleming method will be used to conduct an interim analysis three years after the study. If the study has conducted only once interim analysis, the α level will be set as 0.048 in the final analysis.

4. Safety analysis

Adverse events (AEs) will be summarised using the number of AEs, the number (%) of participants with AEs by groups.

5. All analyses will be performed with a two-sided significance level of 0.05 and conducted using SAS software, version 9.4 (SAS Institute).

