5.3.5 Statistical analyses

All statistical analyses will be performed with a two-sided significance level of 0.05 and conducted using SAS software, version 9.4 (SAS Institute).

VI. Quality of life questionnaire

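### The log-rank test is named as the test of the 8-point non-inferiority hypothesis, but it tests equality of the curves; the confidence-limit rule beside it should be the sole primary test

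*Combined protocol and SAP*

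**What the plan says.** Section 5.3.2 a) states the design: "This study is non-inferiority trial design, and the primary outcome is the rate of OS at 5 years". The null hypothesis is that open minus minimally invasive 5-year OS is at least the margin, and the margin is 8%.

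Section 5.3.2 b) plans Kaplan-Meier curves and then gives three statements in a row:

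- the test: "The logrank test will be used to test the above hypothesis";
- the estimate: "the 5-year OS rate difference and its 95% confidence interval (CI) for the comparison between the two groups will be estimated";
- the success criterion: "The minimally invasive surgery will be considered non-inferior to the open surgery if the one-sided 95% upper limit is less than" the 8% margin.

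Section 3.12 gives the basis of the sample size: "The sample size is calculated based on the difference between the two groups of 5-year OS rate". It assumes 72% in the open group, an 8% margin, 80% power and "a one-sided alpha of 0.025, the sample size estimation resulted in 495 subjects per group".

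Two further statements bear on the level. Section 5.3.3 d) says that after one interim analysis the alpha "level will be set as 0.048 in the final analysis". Section 5.3.5 says: "All statistical analyses will be performed with a two-sided significance level of 0.05".

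**The concern.** The only hypothesis to which the log-rank sentence can refer is the 8-point one. The ordinary log-rank null is equal hazards over the whole of follow-up. Rejecting it in one direction shows that minimally invasive surgery is worse, and in the other that it is better. Failing to reject it shows neither equality nor non-inferiority. A log-rank test with a shifted null exists for non-inferiority, but it needs a hazard-ratio margin and none is stated.

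As written, the p-value labelled as the primary test, read at the blanket two-sided 0.05, answers a different question from the confidence-limit rule two clauses later. Nothing in the plan says that a non-significant log-rank will be taken as non-inferiority, but the wording leaves room for it. Section 5.3.1 calls this text an overview and promises a detailed SAP, which could carry the wording forward.

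**Working it through.** **1. Which test the sample size was built for.** The inputs from section 3.12 are 72% in the open group, margin 0.08, one-sided alpha 0.025 and 80% power. An equal true rate of 72% in the other arm is implied rather than stated.

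n per group = (z₁₋α + z₁₋β)² × 2p(1−p) / margin²

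- 2 × 0.72 × 0.28 / 0.08² = 63.0.
- One-sided 0.025: (1.95996 + 0.84162)² × 63.0 = 494.5, so **495**, as stated.
- Drop-out: 495 / 0.90 = 550 per group, 1100 in total; rounded up to a multiple of 6 this is 1104, as stated.
- One-sided 0.05 would give 389.5, so 390.
- A two-sided test of equality, 72% vs 64%, would give 533 (558 with continuity correction).

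The stated size is a rate-difference non-inferiority calculation at one-sided 0.025.

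**2. A shifted log-rank would not fit this sample size.** Under proportional hazards the 8-point margin corresponds to HR = ln 0.64 / ln 0.72 = 1.36. Schoenfeld's formula gives 4 × (1.960 + 0.842)² / (ln 1.3585)² ≈ 335 deaths. With 990 patients at 28% mortality, 277 deaths are expected, which gives about 72% power.

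**3. How far apart the two procedures are.** With 495 per group at 72%, SE of the difference = √(2 × 0.72 × 0.28 / 495) = 0.0285. The largest observed deficit that still meets the limit rule is:

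- 97.5% limit: 0.08 − 1.960 × 0.0285 = 2.4 points;
- 95% limit: 0.08 − 1.645 × 0.0285 = 3.3 points.

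A significant log-rank needs a deficit of very roughly 1.960 × 0.0285 = 5.6 points. An observed deficit between these values is non-significant on the log-rank and fails the limit rule.

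**4. Simulation.** Assumptions: 552 per arm, exponential survival, every patient followed for 5 years, exponential drop-out of 10% by 5 years, Kaplan-Meier difference at 5 years with Greenwood variance, log-rank at two-sided 0.05, 10,000 trials per scenario (Monte Carlo SE at most 0.5 points).

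| True 5-year OS (open vs minimally invasive) | Log-rank non-significant | 95% limit below 8% | 97.5% limit below 8% |
|---|---|---|---|
| 72% vs 72% | about 95% | 89.4% | 81.8% |
| 72% vs 68% | 70.7% | about 40% | about 29% |
| 72% vs 64% | 20.1% | 5.0% | 2.5% |

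The entries marked ‘about’ come from a separate check of 4,000 trials per scenario under the same assumptions, which also agreed with the other entries.

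At 72% vs 64% a 97.6% limit gives 2.4%. Without drop-out the log-rank figure there is 17.9%, and the 95% and 97.5% limit rules give 5.0% and 2.8%. At 72% vs 68% the log-rank is non-significant while the limit rule is not met in 30% of trials (95% limit) or 41% (97.5% limit).

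At true equality, where non-inferiority holds, the log-rank rejects at only its nominal rate of about 5%. A rejection therefore cannot serve as the demonstration of non-inferiority.

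**5. The levels in the plan.**

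| Section | Level | One-sided equivalent |
|---|---|---|
| 3.12 | one-sided 0.025 | 0.025 |
| 5.3.2 b) criterion | one-sided 95% limit | 0.05 |
| 5.3.2 b) reported interval | 95% CI, upper bound if two-sided | 0.025 |
| 5.3.3 d) | 0.048 after one interim | 0.024 if two-sided |

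At one-sided 0.024 the sample size formula gives 500.6, so 501 per group. Keeping 495 gives power Φ(0.08 / 0.02854 − 1.977) = 79.6%.

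**The case against.** The strongest reply is that the decision rule is already there. The limit sentence is the only one that defines success, and it matches both the hypothesis and the sample size. The log-rank clause has no decision attached to it and may be no more than a loosely worded list of methods. On that reading the plan's false non-inferiority rate is that of the limit rule whatever the log-rank shows, and the 20%, 30% and 41% only show that two tests with different nulls disagree. This stands, and it is why the point concerns a misnamed test and not a missing route to non-inferiority. It does not make the clause correct: the sentence explicitly assigns the log-rank to the stated hypothesis.

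Second, the conflict of levels is a separate defect, and the 5.0% against 2.5% comes from that conflict and not from the log-rank. This is also true. It has to be settled in the same edit, because making the limit rule the sole test at its written level would fix the error rate at twice the design value.

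Third, the figures assume 5 full years for everyone. Section 2.1 gives enrolment from April 2021 to April 2024 and follow-up to April 2026, although section 11.2 says at least 5 years are needed. If April 2026 were a hard cut-off with uniform accrual (an assumption), power at 72% vs 72% would fall from about 82% to about 44% with a 97.5% limit, and from about 89% to about 56% with a 95% limit. Log-rank non-significance at the boundary would rise to about 32%. That is a problem of power and follow-up to be raised separately. It does not alter which test fits the hypothesis.

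**Conclusion.** The concern holds and should be fixed. The log-rank test as named does not test the 8-point hypothesis, while the confidence-limit rule does and is what the 495 per group was calculated for.

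The consequence depends on use. If the log-rank p-value is only reported beside the limit rule, the decision is unaffected. If non-significance were read as non-inferiority, the error at 72% vs 64% would be about 20% (18% without drop-out), against a design level of 2.5%. These percentages rest on exponential survival with full 5-year follow-up. The mismatch between test and hypothesis rests on no numerical assumption. The margin symbols missing from section 5.3.2 are treated as lost in text extraction and play no part in this conclusion.

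**What to change.** - In section 5.3.2 b), delete the clause assigning the log-rank test to the hypothesis. State that the null hypothesis is tested solely by comparing the upper confidence limit of the Kaplan-Meier 5-year OS difference (open minus minimally invasive, Greenwood variance) with 8%.
- State one one-sided level for that limit and use it in sections 3.12, 5.3.2, 5.3.3 d) and 5.3.5. One-sided 0.025 matches the design. If the 0.048 is two-sided and applies to the final primary analysis, the level is 0.024, i.e. a 97.6% limit.
- Keep the log-rank p-value as a supportive comparison of the curves, with no role in the non-inferiority decision.
- Carry the same wording into the detailed SAP.

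The cost is one sentence and one stated level. The Kaplan-Meier curves, the difference and its interval are already planned. The 1104 patients can stay: 495 evaluable per group gives 80.0% power at one-sided 0.025 and 79.6% at 0.024, where an exact 80% would need 501.

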2.3 Prognosis

The main prognostic factors affecting squamous cervical cancer include tumor stage, lymph node status, tumor size, depth of cervical interstitial infiltration, LVSI (lymphovascular interstitial infiltration), and histological type and grading of the tumor. Tumor stage is the most important prognostic factor, followed by lymph node status. After radical cervical cancer surgery + lymph node dissection for clinical stage IB or IIA patients, the 5-year OS was 88-96% for those without lymph node metastasis, while it was 64-74% for those with lymph node metastasis [41, 42]. The 2018 LACC trial found that in stage IA1 with LVSI, IA2 and IB1 cervical cancer patients, the PFS and OS rates of patients receiving minimally invasive radical cervical cancer surgery were lower than those of receiving open surgery, with a PFS rate of 91.2% vs. 97.1% at 3 years, and an OS rate of 93.8% vs. 99.0% at 3 years for minimally invasive surgery versus open surgery, respectively [12]. In contrast, another retrospective study in 2018 found [11] that the relative survival of patients with cervical cancer decreased by 0.8% per year in the 4 years since the use of minimally invasive surgery began in 2006. Therefore, the NCCN guidelines no longer recommend minimally invasive radical cervical cancer surgery. To

sum up, the 5-year overall survival rate for stage I cervical cancer is about 90% and for stage II cervical cancer is about 60%.

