4.1 Allocation of the interventions

4.1.1 Allocation sequence generation: In this study, a centralized block randomization with a block size of 6 will be used to randomly assign patients to the laparoscopic surgery group or the open surgery group at a 1:1 ratio. The randomization scheme will be completed by an independent statistical team at the Clinical Trial Center of the Children's Hospital of Fudan University by creating and sequencing random seed numbers (SAS 9.4 software). The intervention protocols determined by the random assignment sequence will be in sequentially numbered, non-transparent, sealed envelopes by zone: each of the 6 subgroups for each zone will be placed sequentially in six small, non-transparent, sealed envelopes numbered from 1 to 6, and then uniformly placed in the same large envelope marked with the corresponding zone number. The randomization assignment will be administered by the central coordinator at the Obstetrics and Gynecology Hospital of Fudan University who is not involved in the implementation of the intervention or the outcome observation. The enrollment is competitive, and the sub-center coordinator will contact the central coordinator before the inclusion of the first patient in each group. The central coordinator will follow the randomization scheme and assign the large envelopes with the group numbers to each center following the order of contact. Each sub-center will open the envelopes according to the order of signing the informed consent form, and strictly follow the numbered order of the envelopes, and then inform the participating physicians of the assignment scheme and complete written registration form.

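### Randomisation is in effect blocked within centre, but no planned analysis accounts for centre, so the intervals for differences are somewhat too wide if centres differ in outcome

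*Combined protocol and SAP*

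**What the plan says.** **Randomisation (4.1.1).** Allocation is 1:1 in blocks of six. The six small envelopes of a block go into one large envelope, and the central coordinator will "assign the large envelopes with the group numbers to each center following the order of contact". Each centre then opens its envelopes in numbered order as patients consent. Section 11.1 lists six centres. Centre is never called a stratification factor, and nothing in 4.1.1 blocks or stratifies by stage.

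**Primary analysis (5.3.2 b).** Kaplan-Meier curves and a logrank test are planned, and "the 5-year OS rate difference and its 95% confidence interval (CI) for the comparison between the two groups will be estimated". No strata or covariates are named.

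**Other analyses.** The adjusted Cox model in 5.3.2 c) uses blood loss, operative duration and postoperative pain score. Stage appears once, in the subgroup Cox analysis of 5.3.2 d). In 5.3.3 a) the PFS Cox model names no strata. In 5.3.3 b) continuous outcomes use a "generalised linear model (GLM) with treatment as fixed effect and with normal distribution and identity link function"; 5.3.3 c) has the same single term, with a binomial distribution, for binary outcomes. Section 5.3.1 calls all this an overview and says that a detailed SAP will follow.

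**The concern.** Because whole blocks stay in one centre, each centre contributes equal numbers to the two arms, apart from its last unfinished block, which can be out of balance by at most three. A centre with good or poor results therefore moves both arms alike, and its effect cancels from the treatment difference. An unstratified standard error does not know this: it still counts the spread between centres as noise. If centres differ, the interval for a difference is wider than it should be.

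Non-inferiority is decided here by one confidence limit at 80% planned power, so unnecessary width costs power that the randomisation has already provided. The same applies to the surgical outcomes. For these, centre differences are plausible because the protocol leaves much to the operator or centre: robotic or conventional laparoscopy (3.1), type of incision and use of a drain (3.2), instruments and number of ports (3.3). The covariates in 5.3.2 c) are all measured after randomisation and cannot stand in for centre.

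**Working it through.** **1. The plan's own figure.** Inputs from section 3.12: "the 5-year OS rate of 72% in the open surgery group", "a non-inferiority margin of 8" percentage points, 80% power, "a one-sided alpha of 0.025". I assume 72% in both arms.

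n per arm = 2 × 0.72 × 0.28 × (1.960 + 0.842)² / 0.08² = 495. Then 495 / 0.9 = 550 per arm, or 1100 in total, rounded up to a multiple of six = 1104. Both stated figures are reproduced.

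**2. Unstratified precision at 495 per arm.** SE = √(2 × 0.2016 / 495) = 2.85 points. The 95% half-width is 1.96 × 2.85 = 5.59 points. Power = Φ(0.08 / 0.0285 − 1.96) = 80.0%.

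**3. Taking centre out.** Let s be the SD of true 5-year OS between centres. The documents give no value, so the range is assumed. The variance per patient that still affects the contrast is 0.2016 − s². With R² = s² / 0.2016, the unstratified interval is too wide by the factor 1/√(1 − R²), and its actual one-sided error is 1 − Φ(1.96 / √(1 − R²)).

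| Assumed s (points) | Stratified half-width (points) | Unstratified too wide by | Power if stratified | Actual one-sided error, unstratified |
|---|---|---|---|---|
| 0 | 5.59 | 0 | 80.0% | 0.0250 |
| 3 | 5.58 | 0.2% | 80.2% | 0.0247 |
| 5 | 5.56 | 0.6% | 80.5% | 0.0243 |
| 8 | 5.50 | 1.6% | 81.3% | 0.0232 |
| 10 | 5.45 | 2.6% | 82.0% | 0.0222 |
| 15 | 5.27 | 6.1% | 84.5% | 0.0188 |

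Example, s = 10: 0.2016 − 0.0100 = 0.1916; SE = √(2 × 0.1916 / 495) = 2.78 points; half-width 5.45.

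**4. Check by simulation.** 20,000 runs per setting; six centres of unequal size; complete blocks of six; 492 per arm; survival at 5 years as a binary outcome without censoring.

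- No centre differences: stratified and unstratified results agree (power 80.2% for both).
- Centre rates spanning 20 points (SD about 7.6): mean unstratified SE 2.859 against a true 2.798; stratified SE 2.821; power 80.1% unstratified, 81.0% stratified.
- Centre rates spanning 35 points (SD about 12.8): mean unstratified SE 2.860 against a true 2.740; power 80.7% and 82.9%; rejection at the margin 0.019 and 0.023.

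**5. Continuous surgical outcomes.** With a share ICC of the variance between centres, the ratio of unadjusted to adjusted width is 1/√(1 − ICC): 1.026 at an assumed 5% and 1.118 at an assumed 20%.

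**6. Stage, as a separate matter.** With an assumed IB3-IIA2 gap d in 5-year OS and an equal split, the variance explained is 0.25 × d². Power with adjustment is 80.5% at d = 10 points, 81.1% at 15 and 82.0% at 20, against 80.0% without.

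**The case against.** **The effect is small and safe.** This stands. Over an assumed SD of 3 to 10 points the loss for OS is at most 2.0 points of power, and it is zero if centres do not differ. The actual error rate falls below 0.025, so the omission cannot create a false non-inferiority claim, and the estimate stays unbiased.

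**The text is only an overview.** In part. For the GLMs, 5.3.3 specifies treatment as the model term, which is more than silence. For the primary difference the plan is merely silent. Either way, the promised SAP is where the change belongs.

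**Stratification has its own problems.** This stands in part. Enrolment is competitive, so some centres may be small. Inverse-variance weights fail in strata with few or no deaths, where the estimated variance approaches zero. That argues for other weights and a pooling rule, not for ignoring centre. Stratifying a Cox model does not generally narrow the interval for the log hazard ratio; the reason to do it there is to match the randomisation.

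**A stronger reading on stage is tempting.** A reader might infer that stage is neglected in the same way, at a larger cost. Section 2.3 (Prognosis) ranks stage as the leading prognostic factor and states that "the 5-year overall survival rate for stage I cervical cancer is about 90% and for stage II cervical cancer is about 60" per cent. A 40:60 mix of 90% and 60% gives 72%, R² = 0.4 × 0.6 × 0.30² / 0.2016 = 0.107, and power of 84.3%. The documents do not support this reading:

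- Randomisation is not blocked on stage, so an unadjusted interval is correctly calibrated with respect to it.
- Section 5.3.2 d) does use stage, though only in a subgroup analysis.
- The 90% and 60% describe stages I and II overall, whereas this trial enrols only IB3 and IIA2.
- The 40:60 mix is solved backwards from 72% and confirms nothing.

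**Conclusion.** The point holds for centre. The trial randomises in blocks that stay within centres, and nothing in 5.3.2 or 5.3.3 accounts for centre. The unstratified intervals for the 5-year OS difference and the GLM differences are therefore too wide to the extent that centres differ. For the primary endpoint this is a modest efficiency loss: an SD of 15 points between centres would be needed to reach 6.1% excess width and about 4.4 points of power. The larger effect is plausibly on operating time, blood loss and stay. All these sizes rest on assumed between-centre variation. The power figures use the one-sided 0.025 of section 3.12; the relative widths do not depend on that choice.

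Stage is not part of the defect. Adjusting for it is an optional gain whose size depends on an unknown IB3-IIA2 gap.

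**What to change.** In the SAP:

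- **5.3.2 b):** estimate the 5-year OS difference as a weighted average of within-centre Kaplan-Meier differences, with Mantel-Haenszel or sample-size weights rather than inverse-variance weights. State in advance how small centres are pooled. Stratify the logrank test by the same centre groups.
- **Cox models in 5.3.2 and 5.3.3 a):** stratify by centre.
- **5.3.3 b):** add centre as a fixed effect.
- **5.3.3 c):** replace the treatment-only model with a centre-stratified risk difference.
- **Optional:** pre-specify stage at entry (IB3 or IIA2) as a baseline adjustment factor, described as such. Crossing six centres with two stages gives 12 strata, so the pooling rule would have to cover these too.

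The cost is SAP wording and a few lines of SAS, with no new patients or data. The downside is the pooling rule for sparse centres, which should be fixed before outcome data are seen.

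### The non-inferiority rule in 5.3.2 b) tests at one-sided 0.05, twice the one-sided 0.025 for which the trial was sized

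*Combined protocol and SAP*

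**What the plan says.** Four places in the combined protocol and SAP bear on the error rate of the primary comparison.

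- **Section 3.12 (Sample size)** assumes "the 5-year OS rate of 72% in the open surgery group", "a non-inferiority margin of 8" percent, 80% power and "a one-sided alpha of 0.025". It arrives at 495 per group, and at 1104 in total after 10% drop-out and rounding to blocks of six.
- **Section 5.3.2 b)** holds the only sentence that says when success is declared: "The minimally invasive surgery will be considered non-inferior to the open surgery if the one-sided 95% upper limit is less than" the margin, which the same section puts at 8%. The sentence before it asks for the 5-year survival difference with a 95% confidence interval and does not give its sidedness.
- **Section 5.3.3 d)** plans one O'Brien-Fleming interim at three years, after which the alpha "level will be set as 0.048 in the final analysis". Sidedness is not given here either.
- **Section 5.3.5**, repeating a line at the end of 5.3.3, says: "All statistical analyses will be performed with a two-sided significance level of 0.05".

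**The concern.** One-sided 0.025, two-sided 0.05 and two-sided 0.048 (0.024 per side) belong together: the first two are the same threshold, and the third is that threshold after a small allowance for an interim look. A one-sided 95% limit is a one-sided 0.05 test. It fits none of the three, is the most lenient of the four statements, and carries no allowance for the interim.

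The rule governs the primary endpoint, 5-year overall survival. The error at stake is to call minimally invasive surgery non-inferior when it costs 8 points of survival or more. Sections 2.2.1 and 2.3 cite a randomised trial in which survival was worse with this approach (3-year overall survival 93.8% against 99.0%). That trial enrolled earlier stages (IA1 with LVSI, IA2, IB1) than the IB3 and IIA2 patients here, so it does not predict the result. It does show why a false claim of non-inferiority is the error to guard against.

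**Working it through.** **Inputs.** From 3.12: 72% in the open group, margin 0.08, 80% power, one-sided alpha 0.025, 10% drop-out, blocks of six, 552 per group. The same 72% is assumed in the laparoscopic group, since no other rate is given.

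**1. Reproduce the sample size.** n per group = (z₁₋α + z₀.₈₀)² × 2 × 0.72 × 0.28 / 0.08², and 2 × 0.72 × 0.28 / 0.08² = 0.4032 / 0.0064 = 63.

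| One-sided alpha | Calculation | n per group |
|---|---|---|
| 0.025 | (1.960 + 0.842)² × 63 = 494.5 | 495, as stated |
| 0.05 | (1.645 + 0.842)² × 63 = 389.5 | 390 |
| 0.024 | (1.977 + 0.842)² × 63 = 500.6 | 501 |

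Then 495 / 0.9 = 550 per group, or 1100 in total, and the next multiple of six is 1104. Both stated figures reproduce. Taking the null variance at 72% and 64% instead gives 520 at 0.025 and 408 at 0.05, so 495 matches only one-sided 0.025 with the simple variance.

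**2. Error at the margin.** If the true difference is exactly 8 points, a one-sided 95% upper limit falls below 8% with probability 0.05, and a one-sided 97.5% limit with probability 0.025. The ratio is 0.05 / 0.025 = 2.0, or 0.05 / 0.024 = 2.08 against the post-interim level. A simulation of 3,000 trials at the margin (552 per arm, 10% drop-out, full 5-year follow-up) gave 4.9% and 2.4%. The Monte Carlo standard errors are about 0.4 and 0.3 points.

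**3. Largest observed deficit that passes.** Evaluable per arm: 552 × 0.9 ≈ 497. SE = √(0.4032 / 497) = 0.02848.

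- One-sided 97.5% limit: 0.08 − 1.960 × 0.02848 = 0.024, or 2.4 points.
- One-sided 95% limit: 0.08 − 1.645 × 0.02848 = 0.033, or 3.3 points.

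An observed deficit between these values passes under one reading and fails under the other.

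**4. Sidedness of 0.048.** The plan gives no information fraction for the interim. For a classical two-look O'Brien-Fleming design with total two-sided 0.05:

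| Information fraction (assumed) | Final two-sided level |
|---|---|
| 0.3 | 0.0499 |
| 0.4 | 0.0492 |
| 0.5 | 0.0480 |
| 0.6 | 0.0464 |
| 0.7 | 0.0446 |

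The stated 0.048 is the two-sided value at one half.

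**5. Effect of the interim on the written rule.** With an O'Brien-Fleming-type spending boundary at the interim and the one-sided 95% limit at the end, overall one-sided error is 0.050 to 0.051 for information fractions from 0.3 to 0.7. The doubling comes from the final limit; the interim adds at most about 0.1 point.

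**6. Power once the limit is aligned.** With 497 per arm, 0.08 / 0.02848 = 2.809. At one-sided 0.025, Φ(2.809 − 1.960) = 80.2%. At 0.024, Φ(2.809 − 1.977) = 79.7%.

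**The case against.** The strongest reply is that the authors meant the upper end of the 95% confidence interval named one sentence earlier. Taken as two-sided, in line with 5.3.3 and 5.3.5, its upper bound is exactly the planned one-sided 0.025. The fact that 495 reproduces only at that level supports this account of the intent. It is plausible, but the rule says one-sided 95%, and a general statement about significance levels does not override the specific criterion for the primary outcome. An analyst who follows the text would compute the lenient limit.

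Three lesser points stand as qualifications.

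- The interim adjustment is not absent from the plan. It is in 5.3.3 d) but is not carried into 5.3.2 b), and its numerical effect is small.
- Reading 0.048 as two-sided is an inference from the adjacent two-sided 0.05 and from the O'Brien-Fleming value at an assumed half of the information. If 0.048 were one-sided, it would still contradict the one-sided 0.025 in 3.12.
- Section 5.3.1 calls this text an overview and promises a detailed SAP. That gives a place for the correction, but does not change what the present text says.

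**Conclusion.** The concern holds. As written, the success rule carries a 5.0% one-sided error at the margin, against 2.5% in the sample-size section and 2.4% implied by the post-interim level. That is about double on either comparison, and it follows from the definition of the limits. The move in the passing threshold from 2.4 to 3.3 points rests on 72% survival in both arms, 497 evaluable patients per arm, complete 5-year follow-up and a normal approximation. The sample size itself is correct and shows that 0.025 was intended. Whatever the authors meant, two readings that give opposite conclusions for some results should not remain open until the data are seen.

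**What to change.** In 5.3.2 b), replace the one-sided 95% upper limit with one of these:

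- if no interim analysis is done, the upper limit of the two-sided 95% confidence interval for the difference (one-sided 97.5%);
- if the single O'Brien-Fleming interim is done, the upper limit of the two-sided 95.2% interval (one-sided 97.6%).

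In 5.3.3 d), state that 0.048 is two-sided and name the information fraction on which it rests. If the interim falls at another fraction, the final level should be recalculated and the limit changed with it. In 5.3.3 and 5.3.5, add that the primary comparison uses the level set in 5.3.2 b), so that the general two-sided 0.05 does not compete with it. Carry the same wording into the detailed SAP.

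The cost is text only. No extra patients are needed: 497 evaluable per arm gives 80.2% power at one-sided 0.025 and 79.7% at 0.024. What is given up is the extra power of the lenient rule (87.7% with 495 per group, against 80.0% at one-sided 0.025), which the design never claimed.
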